4.3.9 Sample Size

Refer to the individual modules for details of sample sizes.

5 STATISTICAL ANALYSIS - CORE

This section provides information on definitions, derivation and analysis/data presentation per domain.

The analyses in this section focus on items that are applicable to all modules and the module specific analyses are described separately within the individual module sections.

5.1 Study Population

The domain study population covers patient disposition, analysis sets, protocol deviations, demographics, baseline characteristics medical history, prior and concomitant medication and study drug compliance.

5.1.1 Patient Disposition and Completion Status

5.1.1.1 Definitions and Derivations

A clear account of the disposition of all patients who enter the study will be provided.

Study patient (i.e., a patient is “enrolled”) is defined as having a signed informed consent available.

The end of study and end of module is defined in protocol Section 4.4

5.1.1.2 Presentation

Patient disposition including screen failures and reason for screen failure will be summarised and listed based on all patients enrolled/screened (i.e. informed consent received) by dose level/cohort or all patients combined as defined by the current relevant tables, figures, listings (TFL) standards. The number and percentage of patients for the following are summarised:

- Patients screened
- Patients assigned to treatment
- Patients who received study treatment and patients who did not receive treatment
- Patients who discontinued treatment

- Patients ongoing in the study at data cut-off (DCO)
- Patients ongoing treatment at DCO
- Patients who terminated study.

In addition, the number and percentage of patients who discontinued treatment and who discontinued the study, including a breakdown of the reason for discontinuation will be presented for all patients.

Discontinuation of treatment and/or withdrawal from study due to COVID-19 will be presented separately.

The number of patients recruited in each country will be presented.

The number and percentage of patients with confirmed or suspected COVID-19 infection will be presented separately, including details on COVID-19 related interruptions impacting on visits and investigational product administration. Listings of patients affected by the COVID-19 pandemic will be presented detailing any affect and impact on the study. Issues reported in the Clinical Trial Management System will be considered for presented in listings as well.

5.1.2 Analysis Sets

5.1.2.1 Definitions and Derivations

For the definitions of the analysis sets refer to the individual modules.

5.1.2.2 Presentation

The analysis sets will be summarised by dose level/cohort and for all patients combined. For the safety analyses, participants will be reported by the actual treatment(s) received and grouped by their assigned target dose level of AZD0466.

Any exclusions from analysis sets will be listed together with the reasons.

5.1.3 Protocol Deviations

5.1.3.1 Definitions and Derivations

Refer to Section [4.3.7](#)

5.1.3.2 Presentation

The incidence of important protocol deviations (IPDs) will be summarised for the ITT analysis set by deviation categories. The number and percentage of patients in the following categories will be summarised:

- Number of patients with at least 1 IPD
- Number of patients with at least 1 pandemic related IPD
- Number of patients with at least 1 IPD, excluding pandemic related IPDs.

A listing is provided with the IPD details.

5.1.4 Demographics

5.1.4.1 Definitions and Derivations

Age is grouped accordingly in the following categories: <50, ≥ 50 - < 65, ≥ 65 - < 75 and ≥ 75 years. Each race category counts patients who selected only that category.

5.1.4.2 Presentation

Demographic will be summarised and listed for all patients in the safety analysis set (SAF) by dose level/cohort and for all participants combined as defined by the current relevant TFL standards. The following will be summarised: age, age group, sex, race, and ethnicity.

Demographics will further be summarized separately for all patients who had confirmed or suspected COVID-19 infection. If less than 5 patients have confirmed or suspected COVID-19 infection, this will be presented in a listing rather than being summarised.

5.1.5 Baseline Characteristics

5.1.5.1 Definitions and Derivations

Body mass index (BMI) will be derived as: $BMI \left(\frac{kg}{m^2} \right) = \frac{weight \left(kg \right)}{[height \left(m \right)]^2}$

5.1.5.2 Presentation

Patient characteristics at baseline (height, weight and BMI) will be summarized for all patients in the SAF. Baseline characteristics are listed and summarised for the FAS by dose level/cohort and for all patients combined as defined by the current relevant TFL standards. The following are summarised: height, weight and BMI.

Patient characteristics will further be summarised separately for all patients who had confirmed or suspected COVID-19 infection. If less than 5 patients have confirmed or suspected COVID-19 infection, this will be presented in a listing rather than being summarised.

5.1.6 Disease Characteristics

5.1.6.1 Presentation

Disease characteristics at baseline will be summarised and listed for all patients in the SAF by dose level/cohort and for all patients combined as defined by the current relevant TFL standards.

Summaries will be produced that present:

- NHL type
- B-symptoms
- Ann Arbor Staging

- Brain involvement
- Spleen involvement
- Bone marrow involvement
- Liver involvement
- Gastrointestinal involvement
- Extranodal involvement
- Bulky nodal disease
- FLIPI and FLIPI-2 score
- International Prognosis Index score
- Simplified MIPI
- Overexpression of cyclin D1
- Chromosome translocation t(11;14)(q13;q32)
- EBV specification
- TP53 mutation
- ALK gene mutation positive
- MYC rearrangement by FISH
- MYC overexpression by immunohistochemistry (IHC)
- CCI rearrangement by FISH
- CCI overexpression by IHC
- CCI overexpression by IHC
- CCI overexpression by FISH

In addition, summaries will be produced that present summary statistics on patients' target lesions (TLS) and non-target lesions (NTLs), sum of target lesions, number of metastatic sites, other.

5.1.7 Medical History and Concomitant Disease

5.1.7.1 Definitions and Derivations

Medical history and surgical history will be coded using Medical Dictionary for Regulatory Activities (MedDRA).

5.1.7.2 Presentation

Medical history, surgical history and concomitant disease will be listed and summarised for the SAF by dose level/cohort and for all patients combined as defined by the current TFL standards.

A separate summary will be presented for patients who had confirmed or suspected COVID-19 infection. If less than 5 patients have confirmed or suspected COVID-19 infection, this will be presented in a listing rather than being summarised.

Previous Disease-related Treatment Modalities

Summaries of the number and percentage of patients who have had previous disease-related treatments will be presented for each type of modality (immunotherapy, cytotoxic chemotherapy, platinum chemotherapy, biologic therapy, experimental therapy, autologous haematopoietic stem cell transplantation, antibody-drug conjugate therapy, allogeneic haematopoietic stem cell transplantation, CAR-T cell therapy and other).

Summaries for the number and percentage of patients who had a certain number of prior regimens and the best response on most recent regimen will be produced.

All summaries on previous disease related treatment modalities will be presented for the SAF by dose level/cohort and for all patients combined.

Prior Anticancer Treatment

The number and percentage of patients who have had prior anticancer treatments will be summarised for the SAF by dose level/cohort and for all patients combined.

5.1.8 Prior and Concomitant Medications

5.1.8.1 Definitions and Derivations

For the purpose of inclusion in prior and/or concomitant medication or therapy summaries, incomplete medication or radiotherapy start and stop dates will be imputed as detailed in section 4.3.8.

Prior medications, concomitant and post-treatment medications are defined based on imputed start and stop dates as follows:

- Prior medications are those taken prior to study treatment with a stop date prior to the first dose of study treatment.
- Concomitant medications are those with a stop date on or after the first dose date of study treatment, and must have started prior to or during treatment so there is at least one day in common with the study treatment.
- Post-treatment medications are those with a start date after the last dose date of study treatment.

Disallowed medications will be identified through medical review prior to any analysis of concomitant medications.

5.1.8.2 Presentation

The number and percentage of patients who took prior and concomitant medications will be summarised by Anatomical Therapeutic Chemical (ATC) classification codes and the

generic term coded by World health organization (WHO) – Drug dictionary for the SAF by dose level/cohort and for all patients combined.

Summary of disallowed concomitant medications will be produced. All prior, concomitant and post study treatment medication data will be listed.

Missing coding terms will be listed and summarised as “Not coded”.

5.2 Endpoint Analyses

This section covers details related to the endpoint analyses such as primary, secondary, other endpoints including sensitivity and supportive analyses. See [Table 1](#) for details.

Efficacy analyses, except for OS, will be based on investigator assessments based on Lugano criteria for malignant lymphoma ([Cheson et al 2014](#))

All efficacy results will also be listed.

All efficacy analyses will be presented by dose level/cohort.

5.2.1 Primary Endpoint – Objective Response Rate

Part B

The primary efficacy endpoint is the objective response rate (ORR) based on the Lugano classification for Non-Hodgkin Lymphoma (NHL) ([Cheson et al 2014](#)).

5.2.1.1 Definition and Derivations

The Objective Response Rate (ORR) is defined as the proportion of patients who achieve either a partial response (PR) or complete response (CR) as determined by the investigator at local site per Lugano criteria prior to any evidence of progression and will be based on the evaluable for response analysis set. A response does not need to be confirmed to be included in the calculation of ORR.

Data obtained from first dose up until progression, or the last evaluable assessment in the absence of progression, will be included in the assessment of ORR, regardless of whether the patient withdraws from therapy. Patients who discontinue treatment without a response or progression, receive a subsequent anticancer therapy and then respond will not be included as responders in the ORR (i.e., the visit contributing to a response must be prior to subsequent therapy for the patient to be considered as a responder).

The ORR will be based on the investigator assessment using all scans, regardless of whether the scan was scheduled or not.

Best objective response (BoR)

If data permits, this endpoint will also be considered for Part A as exploratory.

Best objective response is calculated based on overall visit responses from Lugano assessments by the investigator recorded in the eCRF. It is the best response a patient has had following start of treatment, but prior to starting any subsequent cancer therapy and up to and including Lugano progression or the latest evaluable assessment in the absence of Lugano progression. Categories of BoR will be based on Lugano criteria using the following response criteria (CR, PR, Stable disease [SD], Progressive disease (PD), and Not evaluable [NE]).

5.2.1.2 Primary Analysis of Primary Endpoint: ORR

Summaries will be produced that present the number and percentage of patients with a tumour response (CR/PR) based on the evaluable for response analysis set. ORR will be calculated and a binomial exact two-sided confidence interval at 80% and 95% using the Clopper-Pearson method will be presented for patients in the evaluable for response analysis set. Patients that have missing overall response assessments at all visits are considered as non-responders, and are therefore counted in the denominator of ORR.

BoR will be summarised by number of patients and percentage for each category (CR, PR, SD, PD, and NE). No formal statistical analyses are planned for BoR.

5.2.1.3 Sensitivity Analysis of ORR Endpoint

A sensitivity analysis will be performed on the ORR endpoint as in section [5.2.1.2](#) but with the intent-to-treat analysis set.

5.2.2 Secondary Endpoint: Complete Response

Part B

The Complete Response is a secondary endpoint.

5.2.2.1 Definition and Derivations

CR rate is defined as the proportion of patients who achieve CR, according to the response criteria for malignant lymphoma reported by the investigator.

5.2.2.2 Primary Analysis of Secondary Endpoint: CR

The CR rate will be calculated and binomial exact two-sided confidence intervals at 80% and 95% will be presented for patients in the evaluable for response analysis set.

5.2.3 Secondary Endpoint: Duration of Response

Part B

The Duration of Response (DoR) is a secondary endpoint.

5.2.3.1 Definition

DoR is defined as the time from the date of first documented objective response (CR or PR) until date of first documented disease progression per Lugano classification as assessed by investigator at local site or death (by any cause in the absence of disease progression).

5.2.3.2 Derivations

DoR (months) = (date of PFS event [progression/death] or censoring – date of first objective response + 1) / (365.25/12).

The end of response should coincide with the date of progression or death from any cause used for the PFS endpoint. The time of the initial response is defined as the latest of the dates contributing towards the first visit response of CR or PR. If a patient does not progress following a response, then their DoR is censored on the PFS censoring date. Only patients who have achieved objective response are evaluated for DoR.

5.2.3.3 Primary Analysis of Secondary Endpoint: DoR

Only patients who achieved objective response (CR or PR) will be included in the summaries of DoR. Kaplan-Meier plots of DoR will be presented. The median DoR and two-sided 95% CI will be estimated using the Kaplan-Meier method. In addition, the proportion of patients still responding at 3, 6, and 12 months after initial response will also be presented. This will be based on patients in the evaluable for response analysis set.

Swimmer plots by patient (including non-responders) that clearly show the profile of each patient will be produced.

5.2.4 Secondary Endpoint: Time to Objective Response

Part B

The Time to objective Response (TTR) is a secondary efficacy endpoint.

5.2.4.1 Definition

TTR is defined as the time from first dose until the first documentation objective response.

5.2.4.2 Derivations

TTR (months) = (date of first objective response – date of first dose + 1) / (365.25/12).

Only patients who have achieved objective response (CR or PR) are evaluated for TTR.

5.2.4.3 Primary Analysis of Secondary Endpoint: TTR

The median TTR and two-sided 95% CI is assessed using the Kaplan-Meier method (without censoring because all patients have events). The number of patients with response at different disease assessment timepoints may be provided. This is based patients in the evaluable for response analysis set.

5.2.5 Secondary Endpoint: Progression-free Survival (PFS)

Part B

The Progression Free Survival (PFS) is a secondary endpoint.

5.2.5.1 Definition

PFS is defined as the time from first dose until the date of first documented disease progression, per Lugano classification as assessed by the investigator at local site, or death (by any cause in the absence of disease progression), regardless of whether the patient withdraws from therapy or receives another anticancer prior to Lugano progression.

5.2.5.2 Derivations

PFS (months) = (date of PFS event [progression/death] or censoring – date of first dose + 1) / (365.25/12).

Patients who have not progressed or died at the time of analysis, or have unknown status, are censored at the time of the latest date of assessment from their last evaluable disease assessment. However, if the patient progresses or dies immediately after two or more consecutive missed visits, the patient is censored at the time of the latest evaluable disease assessment prior to the two missed visits. Note: a NE visit is not considered as a missed visit.

Given the schedule visit assessment scheme (i.e., eight-weekly for the first 24 weeks then twelve-weekly thereafter) the definition of 2 missed visits will change.

If the previous assessment is less than study day 113 (i.e., week 16) then 2 missing visits will equate to 18 weeks since the previous assessment, allowing for early and late visits (i.e., $2 \times 8 \text{ weeks} + 1 \text{ week for an early assessment} + 1 \text{ week for a late assessment} = 18 \text{ weeks}$).

If the 2 missed visits occur over the period when the scheduled frequency of assessment changes from eight-weekly to twelve-weekly this will equate to 22 weeks (i.e., take the average of 8 and 12 weeks which gives 10 weeks and then apply the same rationale, hence $2 \times 10 \text{ weeks} + 1 \text{ week for early assessment} + 1 \text{ week for late assessment} = 22 \text{ weeks}$). The time period for the previous assessment is from study days 113 to 168 (i.e., week 16 to week 24).

From week 24 onwards (when the scheduling changes to 12-weekly assessments), two missing visits equates to 26 weeks (i.e. $2 \times 12 \text{ weeks} + 1 \text{ week for an early assessment} + 1 \text{ week for a late assessment} = 26 \text{ weeks}$).

If the patient has no evaluable disease assessments post-baseline or does not have baseline tumour assessment data, they will be censored at Day 1 unless they die within two visits of

baseline (16 weeks plus 1 week allowing for a late assessment within the visit window)
when the death date qualifies as a PFS event.

A summary of censoring rules and the date of PD/death or censoring are given in [Table 2](#) [Summary of Censoring Rules for PFS](#). Note that censoring overrides event in certain specified cases.

Table 2 Summary of Censoring Rules for PFS

| Situation | Date of PD/Death or Censoring | PFS Outcome |
|---|---|-------------|
| Documented Progressive Disease (PD) or death in the absence of progression | Date of earliest documentation of PD or date of death in the absence of progression | Event |
| Either no tumour assessment at baseline or no evaluable assessments post-baseline AND death prior to second scheduled post-baseline disease assessment | Date of death | Event |
| Either no tumour assessment at baseline or no evaluable assessments post-baseline AND no death prior to second scheduled post-baseline disease assessment | Date of first dose (Day 1) | Censored |
| PD or death (in the absence of progression) immediately after ≥ 2 consecutive missed disease assessments as per the protocol specified assessment schedule | Last evaluable progression-free disease assessment prior to missed assessments | Censored |
| On-going with neither PD nor death at the time of analysis or lost to follow-up or withdrawn consent | Date of last evaluable disease assessment | Censored |

Abbreviations: PD = progressive disease; PFS = progression-free survival

The PFS time is always derived based on scan/assessment dates not visit dates.

Disease assessments/scans contributing towards a particular visit may be performed on different dates. The following rules are applied:

- The date of progression is determined based on the earliest of the dates of the component that triggered the progression.
- When censoring a patient for PFS the patient is censored at the latest of the dates contributing to a particular overall visit assessment.

Note: for TLs only the latest scan date is recorded out of all scans performed at that assessment for the TLs and similarly for NTLs only the latest scan date is recorded out of all scans performed at that assessment for the NTLs.

Duration of follow-up for PFS is defined as follows:

Duration of follow-up for PFS (months) = (date of PFS event (progression/death) or censoring – date of first dose + 1) / (365.25/12).

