8.1.2 Imaging Assessments

During the screening period, an FDG-PET scan covering the whole body from base of skull to mid-thigh will be performed to assess the measurability of disease and will serve as baseline (Day -28 to Day -1). Information on extranodal involvement will also be recorded.

Any imaging assessments performed as part of standard of care within 5 weeks of the ICF signature, may be considered as baseline assessments for the study, provided that no anticancer treatment has been administered between the date of the assessment and the start of study intervention (with the only exception of low-dose steroids given for symptom control) and in the absence of significant clinical worsening of the patient based on the Investigator's opinion.

Subsequent radiological assessment, ie, CT scans with contrast (unless contraindicated) covering neck, chest, abdomen, and pelvis and any other disease sites will be performed every 8 weeks (\pm 7 days) until Week 24 (ie, Weeks 8, 16, and 24), every 12 weeks (\pm 7 days) until Week 48 (ie, Weeks 36 and 48), and thereafter every 16 weeks (\pm 7 days) for R/R DLBCL and R/R MCL, and every 24 weeks (\pm 7 days) for R/R FL and MZL.

Positron emission tomography scans covering whole body from base of skull to mid-thigh (or PET/CT scans) are mandatory on Week 8 (\pm 7 days), Week 24 (\pm 7 days), and Week 48 (\pm 7 days), and thereafter once a year to confirm CR or as clinically indicated. Newly documented CT-based CR should be confirmed by a negative PET scan within a window of 14 days; patients with confirmed CR can be subsequently followed up with CT with IV contrast only. More frequent PET-CT scans can be performed when clinically indicated at the Investigator's discretion.

Efficacy assessments will be performed until disease progression or relapse, start of a new anticancer therapy, death, lost to follow-up, or withdrawal of consent, following the schedule indicated in the SoA in the relevant individual modules. If clinically indicated, unscheduled imaging assessments can be performed at any timepoint during the study.

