Table 8 Schedule of Activities for Module 1 Part A and Part B: Cycle 2 and Beyond and Follow-up

| Procedures | Cycle 2 (28 days) | | Cycle 3 and beyond (28 days) | | EoT | Follow-up | | Details in CSP section or appendix |
|--------------------------|-------------------------|---------|----------------------------------|----------------------------|-----|---|-----------------------------------|------------------------------------|
| Day | 1 | 8/15/22 | 1 | 8/15/22 | | Post-treatment FU visit (28 days after last dose) | Q3M after post-treatment FU visit | |
| Visit window | ± 2 days | | | | | ± 7 days | | |
| Physical examination | X | X | X | X | X | | | 8.2.1 |
| Weight | X | D15 | X | D15 | X | | | 8.2.1 |
| Vital signs | X | X | X | X | X | | | 8.2.2 |
| ECOG performance status | X | | X | | X | | | 8.2.5.2 |
| Concomitant medication | X | X | X | X | X | X | | 6.5 |
| Adverse events | X | X | X | X | X | X | | 8.3 |
| Safety ECGs (triplicate) | X | D8 | Even cycles only beginning at C4 | | X | | | 8.2.3, 10.8.2.3 |
| Cardiac MUGA/MRI/ECHO | | D8 | | D8, every 3 cycles from C5 | X | | | 8.2.5.1 |
| Fresh tumour sample | As clinically indicated | | | | | | | 10.8.6.3 |
| Survival status | | | | | | X | X | NA |
| Laboratory test | | | | | | | | |
| SARS-CoV-2 test | X | | X | | | | | 8.2.4 |
| Pregnancy test (WOCBP) | X | | X | | X | | | 8.2.4 |
| Haematology | X | X | X | X | X | | | 8.2.4 |
| Clinical chemistry | X | X | X | X | X | | | 8.2.4 |
| Serum immunoglobulins | | | | | X | | | 8.2.4 |
| Beta-2 microglobulin | | | | | X | | | 8.2.4 |
| Amylase and lipase | X | X | X | X | X | | | 8.2.4 |

| | | | | | | | | |
|--|---|---|---|---|---|--|--|-------------|
| Coagulation | X | X | X | X | X | | | 8.2.4 |
| Cortisol, ACTH, TSH | | | | | X | | | 8.2.4 |
| Troponin I ^a | | | | | X | | | 8.2.4 |
| BNP (or NTproBNP) | | | | | X | | | 8.2.4 |
| Urinalysis | X | X | X | X | X | | | 8.2.4 |
| Disease assessments | | | | | | | | |
| CT scan | Weeks 8, 16, 24, 36, 48 and thereafter every 24 weeks for R/R FL and MZL, and every 16 weeks for R/R MCL and R/R DLBCL, until disease progression | | | | | | | 8.1.2 |
| FDG-PET scan | Week 8, 24 and 48 and thereafter once a year. If confirmed CR, no further PET scans are required. | | | | | | | 8.1.2 |
| Bone marrow biopsy/aspirate | To confirm CR (if prior bone marrow involvement) or as clinically indicated | | | | | | | 8.1.1 |

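### The PFS limit for two missed scans stays at 26 weeks after scans move to every 16 or 24 weeks, so one missed scan turns a documented progression into a censoring

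*SAP*

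**What the plan says.** SAP 5.2.5.2 censors PFS at the last evaluable assessment "if the patient progresses or dies immediately after two or more consecutive missed visits". Table 2 in the same section counts two or more consecutive "missed disease assessments as per the protocol specified assessment schedule".

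The text then converts two missed visits into a gap since the previous assessment. It takes the schedule to be "eight-weekly for the first 24 weeks then twelve-weekly thereafter" and gives three limits:

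- 18 weeks if the previous assessment was before Day 113.
- 22 weeks across the change of frequency: "The time period for the previous assessment is from study days 113 to 168".
- Finally, "From week 24 onwards (when the scheduling changes to 12-weekly assessments), two missing visits equates to 26 weeks". No later limit follows.

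The scan schedule itself is different. The CT row of SAP Table 8 (Section 14) reads "Weeks 8, 16, 24, 36, 48 and thereafter every 24 weeks for R/R FL and MZL, and every 16 weeks for R/R MCL"; the 16-week interval also covers DLBCL. Protocol 8.1.2 has the same intervals, with the 16-weekly one "for R/R DLBCL and R/R MCL, and every 24 weeks" in the indolent types, and a window of ±7 days on each scan.

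DoR inherits these dates (SAP 5.2.3.2): "The end of response should coincide with the date of progression or death from any cause used for the PFS endpoint".

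**The concern.** The limit is meant to be the longest gap that a single missed scan can produce, so that only a longer gap shows two missed scans. That works only if it is built from the intervals patients actually follow. The 12-weekly interval stops at Week 48 but the 26-week limit does not. From a last scan at Week 36, the two intervals ahead already include one of 16 or 24 weeks.

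If the limits are programmed as written, a patient who misses one scan and has progression documented at the next is censored back at the earlier scan. The SAP's own rule does not intend that. The patients affected are by definition those with a documented event, so the censoring may be informative. Losing their events mainly lifts the later part of the PFS curve, and DoR follows. SAP 5.2.5.3 reports PFS every 3 months and SAP 5.2.3.3 reports response lasting 12 months, so affected estimates are planned outputs.

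**Working it through.** **1. Inputs.** Scans at Weeks 8, 16, 24, 36 and 48, then Weeks 64, 80, 96… (MCL/DLBCL) or 72, 96, 120… (FL/MZL), each ±7 days (Protocol 8.1.2, SAP Table 8). Nominal study day = 7 × week + 1, which matches the SAP's Day 113 for Week 16.

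**2. The SAP's own limits.** Limit = next interval + the one after + 1 week early + 1 week late:

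- 8 + 8 + 2 = 18
- 8 + 12 + 2 = 22
- 12 + 12 + 2 = 26

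All three reproduce.

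**3. The same formula on the actual schedule.**

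- Last scan Week 36: 12 + 16 + 2 = 30 weeks (MCL/DLBCL); 12 + 24 + 2 = 38 weeks (FL/MZL).
- Last scan Week 48 or later: 16 + 16 + 2 = 34 weeks; 24 + 24 + 2 = 50 weeks.

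**4. One missed scan, progression at the next scheduled scan.** Each scan can fall on 15 days, giving 15 × 15 = 225 combinations. Censoring here means the gap exceeds the SAP limit.

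| Last evaluable scan | Gap, MCL/DLBCL (weeks) | Gap, FL/MZL (weeks) | SAP limit (weeks) | Censored |
|---|---|---|---|---|
| Week 8 | 14–18 | 14–18 | 18 | 0/225 |
| Week 16 | 18–22 | 18–22 | 18 or 22 | 105/225 |
| Week 24 | 22–26 | 22–26 | 22 or 26 | 105/225 |
| Week 36 | 26–30 | 34–38 | 26 | 224/225; 225/225 |
| Week 48 and later | 30–34 | 46–50 | 26 | 225/225 |

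The single exception at Week 36 is a gap of exactly 26 weeks. The SAP does not say whether a limit must be reached or exceeded. If reaching it is enough, that case is censored too, and so is an FL/MZL patient with no missed scan whose Week 48 to Week 72 gap is exactly 26 weeks.

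**5. The Day 113 and Day 168 cut points.** They ignore the early half of the window.

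- Week 16 window: Day 106–120. A scan on Day 106–112 gets 18 weeks (126 days). Week 36 falls on Day 246–260, so the gap is 246 − 112 = 134 to 260 − 106 = 154 days, or 19.1–22 weeks. Every case exceeds the limit.
- Week 24 window: Day 162–176. A scan on Day 162–168 gets 22 weeks (154 days). Week 48 falls on Day 330–344, so the gap is 330 − 168 = 162 to 344 − 162 = 182 days, or 23.1–26 weeks. Every case exceeds the limit.
- These are 7 early days × 15 = 105 of the 225 combinations. Scans on or after the nominal day are handled correctly (at most 21 weeks against 22, and 25 against 26).

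**6. Size.** The documents give no missed-scan rate, PFS median or follow-up distribution, so these are assumptions: medians of 6, 12 and 18 months; 5, 10 and 20% missed scans; 20% of events are deaths; scan dates uniform within the window; both schedules; 30,000 simulated patients per scenario. The shift is Kaplan-Meier PFS under the SAP limits minus PFS when missed scheduled scans are counted.

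- *Complete follow-up:* −0.7 to 0 percentage points at 6 months, −0.1 to +0.9 at 12, 0 to +2.1 at 18, +0.2 to +4.2 at 24.
- *Follow-up of 6–18 months.* Protocol 10.9.4.1 triggers the final analysis once the last patient could have had 6 months of treatment; the 18-month upper end is assumed. There is then no usable 18- or 24-month estimate.

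| Missed scans | Wrongly censored, % of all PFS events | 12-month shift (points) |
|---|---|---|
| 5% | 1.2–1.8 | +0.2 to +1.1 (5% and 10% together) |
| 10% | 2.0–2.9 | as above |
| 20% | 3.5–5.1 | +0.9 to +1.7 |

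In the shorter follow-up, 67–87% of the wrongly censored events come from the cut points in step 5.

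**The case against.** **Table 2 already states the right rule.** Counting missed assessments on the protocol schedule needs no week limit, and the schedule is in the SAP. A programmer who follows Table 2 makes no error. That stands to this extent: wrong censoring follows if the limits in the text are programmed. But only the text gives worked limits, and the two instructions give different outcomes for the same patient, so Table 2 does not settle it.

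**The cut-point text is ambiguous rather than wrong.** The 22-week limit is introduced for missed visits that straddle the change of frequency, which also describes a Week 16 scan on Day 106–112. Likewise a Week 24 scan on Day 162–168 fits two of the limits. This is fair as to the words, but the day ranges are explicit and assign the shorter limit.

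**The effect is small.** This largely stands. With 6–18 months of follow-up, the post-Week-36 part alone affects about 0.1–0.9% of PFS events at 5–10% missed scans and 0.5–1.4% at 20%. Cohort sizes are redacted. With an assumed 20–40 events, 1.2–2.9% is 20 × 0.012 = 0.2 to 40 × 0.029 = 1.2 patients. A simple 95% interval around 50% with 20–40 patients has a half-width of 1.96 × √(0.25/n), about 15–22 points. The larger shifts at 18 and 24 months need complete follow-up, and the extremes also need 20% missed scans.

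**Extra censoring is merely cautious.** This does not stand. PFS in Protocol 9.4.2 has no missed-visit censoring, so over-censoring moves further from the protocol, and SAP Sections 3 and 9 declare no change to the planned analyses.

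**Conclusion.** The concern holds. From a last scan at Week 36 or later, the 26-week limit censors a progression found at the next scheduled scan after one missed scan, apart from a gap of exactly 26 weeks. The cut points do the same for Week 16 and Week 24 scans done before Day 113 and Day 169. Both contradict the two-or-more rule in the SAP text and in Table 2. This follows from the documents' own schedule and windows and needs no assumption.

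It applies to progression at a scheduled scan, and to deaths beyond the limit with only one scan missed. An event on an unscheduled scan, or a death, within the limit still counts.

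The size does rest on assumptions. At 6–18 months of follow-up and 5–10% missed scans it is 1.2–2.9% of PFS events and +0.2 to +1.1 points in 12-month PFS. It grows with longer follow-up and more missed scans. PFS and DoR are secondary and descriptive, no hypothesis is tested, and ORR is unaffected. It should be corrected before database lock, but it does not threaten the primary conclusion.

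**What to change.** In SAP 5.2.5.2, replace the 12-weekly assumption with the protocol schedule for the Part B cohorts. Then choose one of two rules and make the text and Table 2 agree.

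1. Count missed scheduled scans directly, as Table 2 says.
2. Set the limit by the scheduled visit of the last evaluable scan, and censor only if the gap exceeds it:

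| Last evaluable scan | Starts at study day | MCL/DLBCL (weeks) | FL/MZL (weeks) |
|---|---|---|---|
| Week 8 | – | 18 | 18 |
| Week 16 | 106 | 22 | 22 |
| Week 24 | 162 | 26 | 26 |
| Week 36 | 246 | 30 | 38 |
| Week 48 and later | 330 | 34 | 50 |

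For events at scheduled scans the limits separate one missed scan from two. The shortest gaps after two missed scans are 26, 30, 38/46, 42/58 and 46/70 weeks, all above the corresponding limit. The options can differ for a death. For example, a death 33.5 weeks after a Week 48 scan on the 16-weekly schedule, with two scans missed, stays an event under option 2. Such cases should be rare, but the SAP should name the rule that governs.

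Also state which interval applies to FL Grade 3b. Cohort B3 admits it and Cohort B2 excludes it, so the DLBCL interval is the natural reading. If PFS is derived for Part A, count missed scans there, because the schedule gives no interval after Week 48 for other B-NHL types. Leave the separate 16 + 1 week rule for patients with no post-baseline assessment as it is.

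The cost is SAP text and one lookup table, with no new data. Late PFS and DoR may look slightly shorter.
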